**Table 8: Imaging and Treatment after First Radiologic Evidence of Progressive Disease**

	Clinically Stable		Clinically Unstable	
	Imaging	Treatment	Imaging	Treatment
First radiologic evidence of PD	Repeat imaging at $\geq 4$ weeks to confirm PD	May continue study treatment at the investigator's discretion while awaiting confirmatory scan	Repeat imaging at $\geq 4$ weeks to confirm PD if possible	Discontinue treatment
Repeat scan confirms PD	No additional imaging required	Discontinue treatment	No additional imaging required	N/A
Repeat scan shows SD, PR, or CR a	Continue regularly scheduled imaging assessments every 6 weeks from Week 12 to Week 48 then every 12 weeks thereafter.	Continue study treatment at the investigator's discretion	Continue regularly scheduled imaging assessments every 6 weeks from Week 12 to Week 48 then every 12 weeks thereafter.	May restart study treatment if condition has improved and/or clinically stable per investigator's discretion

a SD, PR, CR is based on new baseline from first evidence of PD.

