## Immune Related Response Criteria

A growing body of literature indicates that radiographic responses to immunotherapy may have different patterns and kinetics than what would be expected with traditional cytotoxic therapies. To account for these differences we will also characterize radiographic outcomes using the immune related response criteria outlined by Wolchok and colleagues [57]. See Appendix 6. This criteria will be used to measure the abscopal response rate and DCR (CR+PR+SD) and determine whether the study should proceed to stage 2 and is worthy of further study during the Simon two-stage study.

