## **Confirmation**

The main goal of confirmation of objective response is to avoid overestimating the response rate observed. For reporting the study outcomes the response rate and confirmed response rate will be made clear. For interval evaluation of response rates during the Simon-two stage study responses do not need to be confirmed for the study to progress. To be assigned the status of confirmed responses must be confirmed by repeat assessments that should be performed no less than 4 weeks after the criteria for response are first met. Longer intervals as determined by the study protocol may also be appropriate. In the case of SD, follow-up measurements must have met the SD criteria at least once after study entry at a minimum interval (in general, not less than 6-8 weeks) that is defined in the study protocol. For PD all results should be confirmed as described in section 8.2.

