## **Duration of Overall Response**

The duration of overall response is measured from the time measurement criteria are met for CR or PR (whichever status is recorded first) until the first date that recurrence or PD is objectively documented, taking as reference for PD the smallest measurements recorded since the treatment started.

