### BASELINE ASSESSMENT USING irRC

**Step 1.** Identify the index lesions (five lesions per organ, up to ten visceral lesions and five cutaneous lesions).

**Step 2.** Calculate the SPD of all of these index lesions:

$$SPD = \sum_i (\text{Largest diameter of lesion } i) \times (\text{Second largest diameter of lesion } i).$$

POST-BASELINE ASSESSMENTS USING irRC

**Step 1.** Calculate the SPD of the index lesions.

**Step 2.** Identify new, measurable lesions ( $\geq 5 \times 5$  mm; up to five new lesions per organ: five new cutaneous lesions and ten visceral lesions).

**Step 3.** Calculate the SPD of the new, measurable lesions.

**Step 4.** Calculate the tumor burden:

$$\text{Tumor burden} = \text{SPD}_{\text{index lesions}} + \text{SPD}_{\text{new, measurable lesions}}$$

**Step 5.** Calculate the change in tumor burden relative to baseline and the change in tumor burden relative to nadir.

**Step 6.** Derive the overall response using the table below.

Overall Response	Criterion
irCR	Complete disappearance of all lesions (whether measurable or not, and no new lesions) confirmed by a repeat, consecutive assessment $\geq 4$ weeks from the date first documented
irPR	Decrease in tumor burden $\geq 50\%$ relative to baseline confirmed by a consecutive assessment $\geq 4$ weeks from the date first documented
irSD	Criteria for irCR, irPR, and irPD are not met; does not require confirmation
irPD	Increase in tumor burden $\geq 25\%$ relative to nadir confirmed by a consecutive assessment $\geq 4$ weeks from the date first documented

irCR = immune-related complete response; irPD = immune-related progressive disease; irPR = immune-related partial response; irSD = immune-related stable disease.

DETERMINATION OF irBOR

Once a patient has completed all tumor assessments, his/her irBOR may be determined:

Condition	irBOR
At least one irCR	irCR
At least one irPR and no irCR	irPR
At least one irSD and no irCR and no irPR	irSD
At least one irPD and no irCR, no irPR, and no irSD	irPD

irBOR = immune-related best overall response; irCR = immune-related complete response; irPD = immune-related progressive disease; irPR = immune-related partial response; irSD = immune-related stable disease.

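### Table 8 footnote a resets the response baseline at first progression and Appendix 6 does not, so on one available reading unreversed progression can count as stable disease in the DCR

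*Combined protocol and SAP*

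**What the plan says.** Section 8.2 requires progression to be confirmed at least 4 weeks later by the criteria in Table 8. For a repeat scan that shows SD, PR or CR, footnote a of that table states: "SD, PR, CR is based on new baseline from first evidence of PD".

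Appendix 6 has no such reset. irPD is a rise in tumor burden of at least 25% "relative to nadir confirmed by a consecutive assessment" at least 4 weeks later. irPR is a fall of at least 50% "relative to baseline confirmed by a consecutive assessment", with the same interval. irSD is the residual class: "Criteria for irCR, irPR, and irPD are not met; does not require confirmation". The best overall response is irSD under the condition "At least one irSD and no irCR and no irPR", so a later irPD does not cancel it.

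Section 10.1 (Immune Related Response Criteria) says of the Appendix 6 criteria: "This criteria will be used to measure the abscopal response rate and DCR (CR+PR+SD) and determine whether the study should proceed to stage 2". Section 10.1 (Duration of Overall Response) keeps the same reference for progression, "taking as reference for PD the smallest measurements recorded since the treatment started". But section 10.1 (Confirmation) also says: "For PD all results should be confirmed as described in section 8.2". That sentence links the efficacy section to Table 8.

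**The concern.** The same repeat scan has two reference points. Appendix 6 asks whether the burden is still at least 25% above the nadir. Footnote a asks how it has changed since the scan that first showed progression. A tumor that grew and then stayed at its new size is confirmed progression under the first rule and unchanged under the second.

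DCR is the Simon endpoint, and the pass marks are low: more than 3 of 30 in the solid tumor cohort and more than 2 of 14 in the lymphoma cohort (section 12.1). A few patients moved from progression to stable disease could change the decision on stage 2, or the conclusion that the regimen merits a randomized trial. The same reading would lengthen PFS by immune-related criteria. It would also leave the response rule and the stopping criterion in section 8 (progression confirmed by irRECIST) able to disagree for one patient.

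**Working it through.** **1. Where the two rules part.** Inputs are the Appendix 6 cut-offs: +25% for irPD and -50% for irPR, on the sum of products of diameters (SPD). Footnote a gives no cut-offs of its own, so I assume these apply to the new baseline. Set baseline and nadir to 100 and the first progression scan to 130 (+30%).

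- Appendix 6: the repeat scan confirms irPD if it is at or above 100 × 1.25 = 125.
- Footnote a: the repeat scan is SD if it lies above 130 × 0.5 = 65 and below 130 × 1.25 = 162.5.
- Conflict: any repeat value from 125 to below 162.5 is confirmed irPD under one rule and SD under the other. Part of that range, above 130, is further growth.

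With a first progression scan of 125 the conflict runs from 125 to below 156.25; with 200, from 125 to below 250.

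**2. Whether this reaches the DCR.** Section 10.1 routes confirmation of progression to section 8.2, and section 8.2 uses Table 8. If the repeat scan is read as SD, progression is not confirmed. irSD needs no confirmation, and one irSD sets the best response when there is no irCR or irPR. The count changes only for a patient with no earlier irSD, irPR or irCR; the simplest case is one whose first on-treatment scan shows progression.

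Section 10.1 has two partial brakes. It counts stable disease when two consecutive scans show it or it lasts four months. That would remove some single-scan reads, but the text does not say which baseline the scans are judged against. It also mentions a minimum interval, in general 6 to 8 weeks from entry. A repeat scan 4 weeks after Day 60 falls at about Day 60 + 28 = 88, already past 8 weeks (56 days).

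**3. ARR and ORR.** If the repeat scan is back at 100 after growth g, its change from the new baseline is 1/(1+g) - 1. From 125 that is -20%, from 150 -33.3%, from 199 -49.7%; all are SD. It reaches -50% only when g is at least 100%, that is, when SPD has doubled. On the 30% longest-diameter rule in section 10.1, g must be at least 1/0.7 - 1 = 42.9%. Under Appendix 6 a return to baseline size is irSD when the nadir is the baseline, so it is already in the DCR.

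The conflict can also remove responses. With baseline 100, nadir 60, first progression 80 (+33%) and repeat 48, the change is -52% from baseline (meets the irPR size criterion) but -40% from the new baseline (SD).

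**4. The plan's own operating characteristics.** With stage 1 limit r1 of n1 and final limit r of n, P(pass) = Σ over x > r1 of Bin(x; n1, p) × P(X2 ≥ r + 1 - x), where X2 is binomial on n - n1 patients.

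- Solid tumor (1/16, 3/30): 0.0478 at p = 0.05 and 0.8067 at p = 0.20.
- Lymphoma (0/7, 2/14): 0.0274 at p = 0.05 and 0.8101 at p = 0.30.

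Both agree with the stated 80% power and one-sided 0.05 limit.

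**5. Sensitivity to relabelling.** Let m be the share of patients without disease control who are read as SD. The documents give no value, so m is assumed. At a true DCR of 5%, the apparent DCR is 0.05 + 0.95m.

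| m | Apparent DCR | P(pass), solid tumor | P(pass), lymphoma |
|---|---|---|---|
| 0 | 0.050 | 0.048 | 0.027 |
| 2% | 0.069 | 0.120 | 0.062 |
| 5% | 0.0975 | 0.277 | 0.138 |
| 10% | 0.145 | 0.566 | 0.309 |

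**The case against.** The best defense is that footnote a was written for patient management only. Section 8.2 is about discontinuation and says its purpose is managing patients and deciding when to stop. The columns of Table 8 are imaging and treatment. The footnote is attached to the row for a repeat scan showing SD, PR or CR, not to the row that confirms progression, so the 130-to-130 patient reaches it only if progression is first taken as unconfirmed. Section 10.1 names Appendix 6 for the endpoints. Clinically unstable patients, and those with biopsy-proven new metastatic lesions, need no repeat scan.

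Much of this stands. It is a reasonable reading, and it means the plan cannot be said to count progression as control. It does not close the gap: the table does not say which reference decides between the two rows, section 10.1 sends confirmation of progression to section 8.2 without qualification, and no sentence limits the footnote's scope.

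A reader might also infer that any tumor returning to baseline size becomes a PR in the ARR. The documents do not support that. It needs at least a doubling of SPD. Section 10.1 sends only progression to section 8.2, while ARR is tied to the immune-related criteria, so no text carries a re-baselined PR into it. Nor is the bias always upward: the 100, 60, 80, 48 case loses a response.

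Finally, section 12.4 calls the efficacy results preliminary and hypothesis generating, and PFS and ORR are exploratory. That lowers the stakes, but the DCR still drives the Simon decision.

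**Conclusion.** Wrong as written, and it should be fixed. The plan gives two reference points for one repeat scan, and a cross-reference in the efficacy section brings both to bear on the DCR. On one available reading, unreversed progression is stable disease and can be counted as disease control in patients with no earlier irSD, irPR or irCR. Within the DCR this error can only add patients. For ARR and ORR the conflict is weaker and has no fixed direction.

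The size is unknown. False-pass probabilities of 12% to 57% (solid tumor) and 6% to 31% (lymphoma) rest on assumed relabelling of 2% to 10% at a true DCR of 5%. They show how sensitive the low pass marks are. A reader might take them as expected error rates, but the documents contain nothing from which a rate could be estimated. If the Appendix 6 references are used throughout, the stated power and type I error stand.

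**What to change.** Add to section 10.1 that DCR, ARR, ORR, PFS and best overall response by the immune-related criteria use the Appendix 6 references throughout: original baseline for response and nadir for progression, including confirmation of progression. State there that the new baseline in Table 8 footnote a is not used to classify any endpoint.

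Separately, section 8, section 8.2 with Table 8, and Appendix 6 must be reconciled for treatment continuation. The endpoint wording should stay out of Table 8, because that table also triggers discontinuation; no position is taken here on that clinical rule.

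The endpoint change costs a sentence or two in section 10.1 and needs no new scans or patients. The reported DCR may be slightly lower.

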## 9. STUDY ASSESSMENTS AND MONITORING

The study calendar lists all the study assessments and their scheduled times. All data obtained from these assessments will be recorded in the study specific case report forms that will be generated prior to study activation. See Appendix 2 for study registration guidelines and Appendix 3 for data submission schedule.

### 9.1 Study Calendar

Assessment Window (Days)	Screening Days -28 to -1	Days 1, 8, 15, 22, 29 (±7days)	q 60 Day Visits k (±7days)	Follow-up l
Signed Informed Consent Form(s)	X			
Review of eligibility criteria	X			
Medical History	X			
Concomitant medications	X		X	X
Physical examination a	X	X	X	X
ECOG performance status	X	X	X	X
Vital signs	X	X	X	X
Weight	X	X	X	X
Height	X			
Hematology b	X	X	X	X
Serum chemistry b	X	X	X	X
Coagulation panel (aPTT/INR)	X			
EBV, HIV, HBV, HCV serology	X			
C-reactive protein testing	X			
TSH, free T3, free T4	X			
Serum pregnancy test if applicable	X			
Adverse events c		X	X	
Efficacy d			X	X
Investigational Treatment				
Epacadostat e		2x daily administration		
Intralesional SD-101 f		X		
Radiation Therapy g		1 st week		
Tumor Response Assessment				
CT or MRI h	X		X	X
Correlatives				
Blood samples for immune assays		X i	X i	
Biopsy		X j		
Stool Sample		X m		
Abbreviations: ECOG=Eastern Cooperative Oncology Group; EBV=Epstein Barr Virus; HIV=Human Immunodeficiency Virus; HBV=Hepatitis B Virus; HCV=Hepatitis C Virus; TSH=Thyroid Stimulating Hormone; T3=Triiodothyronine; T4=Thyroxine; DLT=dose limiting toxicity; FFPE=formalin-fixed, paraffin-embedded; CT=computerized tomography; RT=radiation therapy.				

- a Patients will be monitored once during the first week of radiotherapy, and with each intralesional SD-101 injection. Patients will be monitored every 30 days (+/- 7 days) thereafter for safety.
- b Hematology and serum chemistry assessments should be obtained within 14 days of the first study treatment and don't need to be repeated on day 1. A complete blood count with differential and a comprehensive metabolic profile should be obtained for these studies. During follow-up these tests will be done every thirty days.
- c Refer to Section 13.5 for procedures for reporting SAEs.
- d ORR, DCR, and PFS will be assessed every 60 days using RECIST 1.1 and irRECIST.
- e Epacadostat: 50-300 mg PO BID throughout the study period until progression.
- f Intralesional SD-101: 4 mg injection into RT treatment lesion. 5 intralesional injections will be administered over a 5 week period on days 1, 8, 15, 22, and 29. The final two injections (on day 22 and 29) are optional for patients with visceral treatment lesions.
- g Radiation therapy: Cohort 1 (solid tumors): 8 Gy × 3 or 4 Gy × 5; Cohort 2 (lymphoma): 8 Gy × 3, 4 Gy × 5, or 2 Gy × 2. All treatments must commence on day 1 after intralesional injection of SD-101. Fractions may be delivered on consecutive or every other day (a minimum of 12 hours and a maximum of 96 hours between treatments), but must be completed during week 1.
- h CT or MRI at pre-treatment and every 60 days throughout the study period.
- i Correlatives: Blood samples for immune assays will be collected on Day 1 and Day 15 and at 60 day clinical visits. See the correlative studies section for detailed information (Section 11.0).
- j Biopsy: On Day 1 and Day 15 tumor biopsy will precede intralesional injection, RT, and epacadostat. See the correlative studies section for detailed information (Section 11.0). NOTE: The Day 1 biopsy and labs must be completed before starting protocol treatment.
- k q 60 Day Visits: Patients will be followed with a imaging, labs, and clinic visit every 60 days during the first year of study. Brief visits for safety monitoring will occur every 30 days (+/- 7 days).
- l Follow-up: All patients will be followed for 30 days after the last dose of treatment with the agent under this IND or until all clinical significant toxicities resolve to baseline or grade ≤ 1. Additional follow-up data will be gathered every 3 months from standard of care follow up visits and assessments after trial discontinuation.
- m Stool sample will be collected from patients before initiation of treatment.

## 10. ASSESSMENTS TYPES

### 10.1 Efficacy

Response and progression will be evaluated in this study using the new international criteria proposed by the revised Response Evaluation Criteria in Solid Tumors (RECIST) guideline (version 1.1) [56] as well as irRECIST criteria. Additionally, imaging will be reviewed by a radiologist in conjunction with a radiation oncologist to help distinguish tumor progression from post-radiotherapy scarring. Changes in the largest diameter (unidimensional measurement) of the tumor lesions and the shortest diameter in the case of malignant lymph nodes are used in the RECIST criteria.

#### Disease Parameters

##### *Measurable Disease*

The presence of at least one measurable lesion. If the measurable disease is restricted to a solitary lesion, its neoplastic nature should be confirmed by cytology/histology.

##### *Measurable Lesions*

Lesions that can be accurately measured in at least one dimension with longest diameter 20mm using conventional techniques or 10mm with spiral CT scan.

##### *Non-Measurable Lesions*

All other lesions, including small lesions (longest diameter <20 mm with conventional techniques or <10 mm with spiral CT scan), i.e., bone lesions, leptomeningeal disease, ascites, pleural/pericardial effusion, inflammatory breast disease, lymphangitis cutis/pulmonitis, cystic lesions, and also abdominal masses that are not confirmed and followed by imaging techniques.

All measurements should be taken and recorded in metric notation, using a ruler or calipers. All baseline evaluations should be performed as closely as possible to the beginning of treatment, preferably within two weeks of treatment initiation, and never more than 4 weeks before the beginning of the treatment.

The same method of assessment and the same technique should be used to characterize each identified and reported lesion at baseline and during follow up.

Clinical lesions will only be considered measurable when they are superficial (e.g., skin nodules and palpable lymph nodes). For the case of skin lesions, documentation by color photography, including a ruler to estimate the size of the lesion, is recommended.

## Methods of Measurements

CT and MRI are the best currently available and reproducible methods to measure target lesions selected for response assessment. Conventional CT and MRI should be performed with cuts of 10 mm or less in slice thickness contiguously. Spiral CT should be performed using a 5 mm contiguous reconstruction algorithm. This applies to tumors of the chest, abdomen and pelvis. Head and neck tumors and those of extremities usually require specific protocols.

Lesions on chest X-ray are acceptable as measurable lesions when they are clearly defined and surrounded by aerated lung. However, CT is preferable.

When the primary endpoint of the study is objective response evaluation, ultrasound (US) should not be used to measure tumor lesions. It is, however, a possible alternative to clinical measurements of superficial palpable lymph nodes, subcutaneous lesions and thyroid nodules. US might also be useful to confirm the complete disappearance of superficial lesions usually assessed by clinical examination.

The utilization of endoscopy and laparoscopy for objective tumor evaluation has not yet been fully and widely validated. Their uses in this specific context require sophisticated equipment and a high level of expertise that may only be available in some centers. Therefore, the utilization of such techniques for objective tumor response should be restricted to validation purposes in specialized centers. However, such techniques can be useful in confirming complete pathological response when biopsies are obtained.

Cytology and histology can be used to differentiate between PR and CR in rare cases (e.g., after treatment to differentiate between residual benign lesions and residual malignant lesions in tumor types such as germ cell tumors).

## Response Criteria

### Evaluation of Target Lesions

- **Complete Response (CR):** Disappearance of the target lesion
- **Partial Response (PR):** At least a 30% decrease in the sum of the LD of target lesions, taking as reference the baseline sum LD
- **Progressive Disease (PD):** At least a 20% increase in the sum of the LD of target lesion, or the appearance of one or more new lesions
- **Stable Disease (SD):** Neither sufficient shrinkage to qualify for PR nor sufficient increase to qualify for PD, taking as reference the smallest sum LD since the treatment started

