**Table 9: Best Overall Response Evaluation**

Best Overall Response Evaluation		
Target Lesion	New Lesion	Overall Response
CR	No	CR
PR	No	PR
SD	No	SD
PD	Yes or No	PD

Patients with a global deterioration of health status requiring discontinuation of treatment without objective evidence of disease progression at that time should be classified as having “symptomatic deterioration”. Every effort should be made to document the objective progression even after discontinuation of treatment.

In some circumstances it may be difficult to distinguish residual disease from normal tissue.

When the evaluation of complete response depends on this determination, it is recommended that the residual lesion be investigated (fine needle aspirate/biopsy) to confirm the complete response status.

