## 17.6 Appendix 6: Immune-Related Response Criteria

Increasing clinical experience indicates that traditional response criteria (e.g., Response Evaluation Criteria in Solid Tumors, Version 1.1 [RECIST v1.1] and World Health Organization [WHO]) may not be sufficient to characterize fully activity in the new era of target therapies and/or biologics. In studies with cytokines, cancer vaccines, and monoclonal antibodies, complete response, partial response, or stable disease has been shown to occur after an increase in tumor burden as characterized by progressive disease by traditional response criteria. Therefore, conventional response criteria may not adequately assess the activity of immunotherapeutic agents because progressive disease (by initial radiographic evaluation) does not necessarily reflect therapeutic failure. Long-term effect on the target disease must also be captured. The immune-related response criteria (irRC) are criteria that attempt to do that by enhancing characterization of new response patterns that have been observed with immunotherapeutic agents (i.e., ipilimumab) [57]. (Note: The irRC only index and measurable new lesions are taken into account.)

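### The printed RECIST rules and Table 9 ignore existing non-measurable disease, which can inflate the RECIST CR label, ORR and PFS; Appendix 6 also leaves such disease out of the DCR count and warrants a supporting tabulation

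*Combined protocol and SAP*

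**What the plan says.** **RECIST rules (Section 10.1).** The Non-Measurable Lesions paragraph names the disease that falls outside measurement, including "bone lesions, leptomeningeal disease, ascites, pleural/pericardial effusion". The response rules that follow appear under Evaluation of Target Lesions. CR is "Disappearance of the target lesion". PD is "At least a 20% increase in the sum of the LD of target lesion, or the appearance of one or more new lesions". Table 9 then builds the overall response from two inputs, the target-lesion result and whether there is a new lesion. No column or rule covers existing non-target or non-measurable disease.

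**Immune-related criteria (Section 10.1 and Appendix 6).** Section 10.1 gives the go/no-go role to the immune-related criteria: "This criteria will be used to measure the abscopal response rate and DCR (CR+PR+SD) and determine whether the study should proceed to stage 2". Appendix 6 states its scope: "The irRC only index and measurable new lesions are taken into account". Tumor burden is the sum of products of diameters over index lesions plus new measurable lesions. irPD is a rise in that burden of at least 25% from nadir. irSD is whatever is not irCR, irPR or irPD, with no confirmation needed. irCR is the exception to the restricted scope, since every lesion must disappear, non-measurable ones included.

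**Use.** Section 12.4 reports responses under both criteria sets. DCR is CR + PR + SD. ORR and PFS are exploratory (Section 1.3).

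**The concern.** The protocol defines a class of disease and then gives its worsening no consequence in the printed scoring rules. Patients with advanced solid tumors or lymphoma can have effusions, ascites or bone disease alongside a measurable target lesion. A reader who scores from Table 9 would record SD, PR or CR for a patient whose disease is plainly advancing outside the measured lesions.

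Two separate consequences should be kept apart:

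- **RECIST results.** The CR label, ORR and PFS can look better than they are.
- **DCR and the Simon decision.** These run on Appendix 6, not Table 9. Growing or new non-measurable disease adds nothing to tumor burden there, so a patient with stable index lesions is irSD and counts as controlled. The null DCR is only 5%, so few such patients are needed to matter.

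**Working it through.** **Step 1. Apply the printed rules to the relevant cases.**

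| Case | Table 9 (RECIST) | Appendix 6 |
|---|---|---|
| Index/target stable, existing non-measurable disease clearly worse | SD | irSD (control) |
| Index/target stable, new non-measurable lesion | PD (any new lesion counts) | irSD (control) |
| Target shrinks to PR, existing non-measurable disease clearly worse | PR | irPR if burden falls at least 50% (control) |
| Target gone, non-measurable disease persists, no new lesion | CR | not irCR |

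Rows 1 and 3 affect RECIST PFS, because no progression event is recorded. Row 3 also affects ORR. Row 4 affects the CR label. Row 4 cannot affect DCR, because CR, PR and SD all count. Rows 1 to 3 show where Appendix 6 counts control despite disease advancing outside the measured lesions.

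**Step 2. Reproduce the plan's design figures.** Inputs from the Schema and Section 12.1 are solid tumor r1/n1 = 1/16 and r/n = 3/30 with p1 = 0.20, and lymphoma 0/7 and 2/14 with p1 = 0.30. In both, p0 = 0.05, one-sided alpha is 0.05 and power is 0.80.

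Pass probability: P(p) = Σ over x = r1+1 to n1 of Pr(Bin(n1, p) = x) × Pr(Bin(n − n1, p) ≥ r + 1 − x).

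Solid tumor at p = 0.05:
- x = 2: 0.1463 × 0.1530 = 0.0224
- x = 3: 0.0359 × 0.5123 = 0.0184
- x ≥ 4: 0.0070 × 1 = 0.0070
- Sum: 0.0478

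The same formula gives power 0.807 at p = 0.20. For lymphoma it gives 0.0274 at p = 0.05 and power 0.810 at p = 0.30. The stated 80% power reproduces, and both designs stay under 0.05.

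**Step 3. Illustrate the Appendix 6 effect.** The documents give no rate for progression confined to non-measurable disease. Assume that DCR excluding such patients is 5%, and that a share s of the remaining 95% have it and are scored irSD. The counted DCR is then p = 0.05 + 0.95s, which goes into the same formula.

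| s (assumed) | Counted DCR | Pass, solid tumor | Pass, lymphoma |
|---|---|---|---|
| 0 | 0.0500 | 4.8% | 2.7% |
| 1% | 0.0595 | 8.0% | 4.3% |
| 2% | 0.0690 | 12.0% | 6.2% |
| 5% | 0.0975 | 27.7% | 13.8% |
| 10% | 0.1450 | 56.6% | 30.9% |

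In a full solid-tumor cohort, s = 5% is 0.0475 × 30 ≈ 1.4 patients, against the four needed to pass.

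**The case against.** **RECIST 1.1 is adopted by citation, so its rules apply to lesions other than targets.** This has some force. The rules in question sit under a heading about target lesions, and silence there need not disapply the cited guideline. It is therefore too strong to say that non-target progression can never count. But the protocol prints its own overall-response table without that input, so a scorer using Table 9 and one using the guideline could classify the same scan differently.

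**Appendix 6 is a deliberate choice.** This stands. The restriction to index and measurable new lesions is stated openly and attributed to a published criterion. Overriding it in the go/no-go count would be a trade-off, not the repair of an error. The plan calls these criteria irRECIST in most places while Appendix 6 describes irRC, but Section 10.1 points to Appendix 6 for the decision.

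**The two CR rules contradict each other.** A reader might infer this. They belong to two criteria sets reported side by side, which also differ on PR (30% of summed diameters against 50% of summed products) and PD (20% against 25%). Different CR rules between two named systems are not in themselves a contradiction.

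**Other provisions catch these patients.** Only in part. Section 10.1 generally asks for two stable scans or four months before calling SD, though its Confirmation paragraph and Appendix 6 are looser. Early deaths and unassessable patients count as failures under Reporting of Results. Symptomatic deterioration is not one of the eight reporting categories listed there, and the clinical-stability criteria in Section 8.2 govern treatment, not scoring. None of these makes worsening non-measurable disease a progression event.

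**Conclusion.** The Table 9 gap is real and goes beyond missing detail: followed as printed, it can bias the RECIST CR label, ORR and PFS upward. The documents do not allow the size to be estimated. These endpoints are exploratory, which limits the consequence.

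A reader might infer that the Table 9 gap inflates DCR and the Simon decision. It does not: the CR gap cannot move DCR, and the decision runs on Appendix 6.

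A reader might also take the pass probabilities in the working as the trial's true false-positive rate. The documents do not support that. The plan sets its 5% null for DCR as measured by the immune-related criteria, and alpha is controlled for that quantity. The higher figures arise only when control is redefined more strictly while the null stays at 5%, and the shares are assumptions. What they do show is sensitivity: one or two patients of this kind could change the solid-tumor decision, so their number should be visible.

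**What to change.** 1. Add a non-target column to Table 9. Overall CR requires disappearance of non-target disease, and unequivocal progression of non-target disease is PD. State the same in the Response Criteria text.
2. Keep the Appendix 6 count for the Simon decision. Beside it, for each cohort, report the number of patients counted as controlled who had unequivocal progression of existing non-measurable disease, or new non-measurable disease, and give DCR recomputed without them.

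The cost is one table column and one extra tabulation from scans already scheduled every 60 days. Sample sizes and Simon boundaries do not change. The RECIST response rates and the supporting DCR may come out slightly less favourable.
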